9.5 Device Reports (AEs)

During the course of the study, AEs which may be attributable to the use of these devices may occur. All events should be collected regardless of whether the event was causally related to the device or not.

Any SAE device reports should be captured using the SAE report form, and submitted to the Pharmacovigilance CRO following the same timelines and procedure as for SAE drug reports. All SAE device reports will be submitted by the Sponsor to the relevant national or international authorities according to the national regulations, directives and timescales in force in the different countries where the study is conducted. A separate document will be produced by the Pharmacovigilance CRO which details all specific reporting requirements.

10 STATISTICS

10.1 Sample size

The trial sample size was calculated to achieve 80% power to reject the null hypothesis $H_0 = "r \leq 70\%"$, using a one-sided exact binomial test with 5% alpha risk.

From historical clinical data, the true response rate is expected to be greater than 90%. However, to remain conservative the true response rate could only be estimated from localized intermediate-risk prostate cancer patients patients who underwent the TOOKAD Soluble procedure and for whom biopsies were available after 12 months. Using these conservative estimates we identified a true response rate is greater than 83.6% with >80% posterior probability (assuming a beta-binomial model).

Using this conservative choice for true response rate $r=83.6\%$ a minimum of $N=44$ patients with fully evaluable data is required.

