This study is a phase IIb trial using optimal dose of TOOKAD® Soluble and optimal light-energy level conditions that were determined in previous phase I and II studies and confirmed by the phase III studies among patients with localized prostate cancer. Partial gland ablation therapy using thermal approaches, as an alternative to radical treatments for low-volume prostate cancer, is a treatment option currently being offered to men with prostate cancer in the U.S. as a tailored means to manage their disease with fewer side effects. Previous studies of TOOKAD® Soluble treatment have suggested that this non-thermal approach is an effective therapeutic strategy to achieve ablation of the prostatic tissue that contains the cancer lesion in this patient population. Considering the available clinical data, a phase IIb is considered appropriate at this stage, with the main aim of confirming, in intermediate risk patients, previous findings in low and favorable intermediate risk prostate cancer patients. Moreover, a single center design was also considered appropriate, as it allows for optimal standardization of the technique and better control over data acquisition.

NUMBER OF PATIENTS:

In order to obtain at least 44 evaluable patients, a total of 50 patients will be included and will be treated with TOOKAD® Soluble VTP in this study.

DRUG DESCRIPTION AND PREPARATION:

TOOKAD® Soluble - padeliporfin di-potassium (WST11) Drug Product is a dark coloured powder for solution for injection. It is packaged in amber glass vials. It is manufactured in two different presentations:

- 200 mg TOOKAD® Soluble in a 30 mL vial with blue flip-off cap, to be reconstituted, just before administration, with 20 mL of 5% dextrose solution for injection
- 400 mg TOOKAD® Soluble in a 50 mL vial with white flip-off cap, to be reconstituted, just before administration, with 40 mL of 5% dextrose solution for injection

The two presentations have the same formulation which is produced in exactly the same process and they differ only in the amount of TOOKAD® Soluble per vial, the size of the vial and the colour of the flip-off cap.

For both presentations the final concentration of TOOKAD® Soluble solution to be injected is 10 mg/mL.

INCLUSION CRITERIA:

Subjects will be eligible for inclusion in the study if all of the following criteria are met:

1. Men over 18 years of age.

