- Patients' reported outcome measures (PROMs) impairment: urinary symptoms using IPSS and erectile functions using IIEF prior to treatment beginning and then 1, 3, 6, 12, 24, 36, 48 and 60 months after completing treatment
- Severe prostate cancer-related events: cancer extension to T3, metastasis or prostate cancer-related death
- Use of secondary prostate cancer treatment following VTP will include surgical removal of the prostate gland, radiation treatment to the prostate gland, use of hormone or chemotherapies.
- Adverse events
- Serum PSA measurements in ng/mL.

SAMPLE SIZE JUSTIFICATION

A proportion of responders of $r=70\%$ at 12 months is considered to be a clinically significant expectation in localized intermediate-risk prostate cancer patients.

Based on historical data in similar series of patients, a minimum of $N=44$ patients is required to test the null hypothesis $H_0: "r \leq 70\%"$ vs. $H_1: "r > 70\%"$, with 80% power and 5% as alpha risk.

MANUFACTURING INVESTIGATIONAL PRODUCT:

TOOKAD® Soluble is manufactured by Praxis Pharmaceutical S.A, Vitoria-Gasteiz, Spain.

TOOKAD® Soluble batches are released by Steba Laboratories, Ness Zion, Israel.

Laser equipment: Intermedic Arfran S.A, Spain

FLOW CHART: Schedule of Events

Procedure	V1 and screening period	V2 VTP	V3 Day 7+/- 2 days	V4 Month 1 +/- 1 wk	V5 Month 3 +/- 2 wks	V6 Month 6 +/- 2 mos	V7 Month 12 +/- 2 mos	V8-11 Annual f/u +/- 3 mos
Informed Consent	X							
Inclusion/exclusion Criteria	X							
Medical History	X							
TNM Staging	X							
VTP Treatment		X						
Clinical Examination	X	X ^a						
Prostate Biopsy	X ^b ≤6mos before consent				X ^c		X	X ^d
Digital Rectal Examination	X							
Prostate Specific Antigen	X ^e	X		X	X	X	X	X
Standard Hematologic Tests	X ^e	X ^a		X	X	X	X	X
Standard Blood Chemistry Tests	X ^e	X ^a		X	X	X	X	X
Standard Blood Coagulation Tests	X ^e							
Additional Inclusion Blood Tests	X ^e							
Prostate Volume	X	X						
MRI	X ^d				X		X	X ^d
Patient-Reported Outcome Measures (PROMs)	X			X	X	X	X	X
Study Medication		X						
Concomitant Medications	X	X ^a	X	X	X	X	X	X
Adverse Events		X ^a	X	X	X	X	X	X

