#### **Planned sample size**

For an assumed true response rate of 83.6%, we can discount a response rate of 70% at a one-sided alpha of 10%, with a power of 80% if we have a sample size of 44 patients.

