### **Primary efficacy analysis**

The proportion of patients with no pattern 4 or 5 found in the 12 month biopsy will be reported along with a one-sided 90% confidence interval. Patients who have pattern 4 or 5 found before 12 months and who receive radical therapy will be treated as treatment failures. The treatment will be considered a success if the lower bound, rounded to 0.01, is 70% or higher. For a sample size of 44, this means that treatment will be declared a success if 35 or more patients respond.

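### The protocol tests the primary endpoint at 5% and the SAP at one-sided 10%, with the same N=44 and 80% power; results of 35 or 36 of 44 pass one and fail the other

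*Protocol*

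**What the plan says.** **Protocol.** Section 10.1 bases the sample size on rejecting a response rate of 70% or less with 80% power, "using a one-sided exact binomial test with 5% alpha risk". It fixes the true rate at 83.6% and concludes that "a minimum of $N=44$ patients with fully evaluable data is required". The synopsis gives the same null hypothesis and N, "with 80% power and 5% as alpha risk". The synopsis also says: "In order to obtain at least 44 evaluable patients, a total of 50 patients will be included".

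**SAP.** Planned sample size keeps 70% and 83.6% but works "at a one-sided alpha of 10%, with a power of 80% if we have a sample size of 44 patients". Under Primary efficacy analysis the responder proportion "will be reported along with a one-sided 90% confidence interval". The decision rule is: "The treatment will be considered a success if the lower bound, rounded to 0.01, is 70% or higher". It continues: "For a sample size of 44, this means that treatment will be declared a success if 35 or more patients respond". No interval method is named.

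The SAP's heading for changes from the protocol's planned analysis has no text under it in the supplied copy.

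**The concern.** When alpha doubles and everything else is held fixed, either the power or the sample size has to move. Here neither does, so at least one of the two design statements is wrong.

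This is the only confirmatory test in an open-label, single-arm trial; protocol 10.4.2 treats the secondary variables descriptively. The inference is the comparison with a threshold. If two governing documents imply different thresholds, a reader cannot tell which was prespecified, and a result that falls between them can be called either way.

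**Working it through.** **Inputs.** p0 = 0.70, p1 = 0.836, N = 44 and power 80% (protocol 10.1; SAP Planned sample size). Alpha is 5%, one-sided exact binomial (protocol 10.1), or 10%, one-sided (SAP). The SAP cutoff is 35/44.

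**Step 1: where 44 comes from.** The one-sample normal approximation is

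n = [(z(1−α)·√(p0(1−p0)) + z(0.80)·√(p1(1−p1))) / (p1 − p0)]²

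with √(0.70×0.30) = 0.4583, √(0.836×0.164) = 0.3703 and p1 − p0 = 0.136.

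- One-sided 10%: [(1.2816×0.4583 + 0.8416×0.3703)/0.136]² = 43.7, so 44.
- One-sided 5%: [(1.6449×0.4583 + 0.8416×0.3703)/0.136]² = 61.4, so 62.

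The SAP's 44 is reproduced at 10%. The protocol's 44 is not reproduced at 5%.

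**Step 2: the exact test at N=44.** Size is P(X ≥ r | 44, 0.70). Power is P(X ≥ r | 44, p).

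| Success at | Size | Power at 83.6% | Power at 90% |
|---|---|---|---|
| 35 or more (SAP) | 10.92% | 82.6% | 99.0% |
| 36 or more | 5.64% | 71.1% | 97.2% |
| 37 or more | 2.55% | 56.4% | 93.2% |

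At 36 the size exceeds 5%, so the protocol's test needs 37. That cutoff reaches 80% power only if the true rate is at least 87.1%. At a true rate of 83.6%, the chance of landing on 35 or 36 is 82.6% − 56.4% = 26.2%.

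**Step 3: can the 50 included patients make up the power?** Exact 5% test, power at 83.6%:

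| N | Cutoff | Size | Power |
|---|---|---|---|
| 44 | 37 | 2.55% | 56.4% |
| 45 | 37 | 4.71% | 68.7% |
| 46 | 38 | 3.92% | 66.2% |
| 47 | 39 | 3.26% | 63.7% |
| 48 | 40 | 2.69% | 61.3% |
| 49 | 40 | 4.80% | 72.4% |
| 50 | 41 | 4.02% | 70.1% |

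No N in this range reaches 80%. The smallest that does is 61 (49/61, size 4.86%, power 80.9%). That figure only shows that 44 is not the minimum for the stated test; it is not a proposal to enrol more.

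**Step 4: the SAP rule against its own 10%.** One-sided 90% lower bounds at 35/44 are 0.6964 (exact, Clopper-Pearson), 0.7076 (Wilson) and 0.7175 (Wald). With the exact bound, 35/44 passes only because 0.6964 rounds to 0.70; unrounded, 36/44 (0.7215) is needed. All three methods give 35 at N=44 once rounded, but they can part elsewhere. At N=50 the rounded rule gives 40 with the exact bound (size 7.9%) and 39 with Wilson or Wald (size 13.9%). With the rounded exact bound, size exceeds 10% at N=44 (10.9%) and N=48 (10.7%) only.

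**The case against.** **The protocol prints no cutoff.** Its 37/44 is derived from the sample-size section, 10.2.1 hands the detailed analysis to the SAP, and the SAP's rule is explicit, so an analyst following the SAP knows what to do at N=44. This is true, but the 5% is stated twice in the protocol and tied to the test of the null hypothesis. A result of 36/44 has an exact p-value of 0.056 and fails that test. Delegating detail does not delegate an unrecorded change of alpha.

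**83.6% is deliberately pessimistic.** Section 10.1 expects more than 90% and takes 83.6% as a conservative value from a beta-binomial model. If one assumes a flat prior and the 8 of 8 evaluable Gleason 3+4 patients in protocol 2.2.4, the posterior is Beta(9,1) and P(rate > 0.836) = 0.80, which matches the text. Averaged over that posterior, the 37/44 rule has 80.0% power. This lessens the practical weight of the 56%, and at a true rate of 90% power is 93.2%. It does not rescue the statement, because 10.1 says that N was computed at a fixed 83.6%.

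**The rounding rule is prespecified and 10.9% is close to 10%.** This stands. The interval method is a secondary point at N=44, and it gains weight only if the analysed N differs.

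**Versions.** The SAP cites protocol version 6.0, the version of the supplied protocol cannot be confirmed, and parts of both files are not in the supplied copy. A reason for the change may be recorded elsewhere.

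**Conclusion.** The concern holds, and it must be fixed. As supplied, the two documents set different alphas for the same test with the same N and claimed power. The protocol overstates power by about 24 percentage points at its own design rate (80% against 56.4%), and the SAP's cutoff has about twice the type I error that the protocol allows (10.9% against 5%). The verdicts differ at 35 and 36 of 44.

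The size and power figures are exact binomial and use only rates and counts stated in the documents. The verdict rests on reading 10.1 literally (one-sided exact test, fixed 83.6%) and on the documents as supplied.

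**What to change.** Before month-12 results are read, put one alpha, one named interval method and one cutoff rule in the protocol synopsis, protocol 10.1, and the SAP's Planned sample size and Primary efficacy analysis. Record the change under the SAP's heading for changes. The choice of alpha is the sponsor's:

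- **If 5% stands:** use an unrounded exact one-sided 95% bound, set the cutoff at 37/44 (bound 0.7219; 36/44 gives 0.6958), delete the rounding rule and the sentence giving 35, and restate power as 56% at 83.6%.
- **If 10% is intended:** amend the synopsis and 10.1 to one-sided 10%. Then either (a) use the unrounded exact bound with 36/44 (size 5.6%, power 71.1%), or (b) keep 35/44, name the interval method, and state the actual size (10.9%) and power (82.6%).

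In each case, state that the cutoff is recomputed by the same rule if the analysed N is not 44. Under the unrounded exact rule at 10% this gives 36/45 (size 9.3%, power 80.7%) and 40/50 (size 7.9%, power 81.3%); at 5% it gives 41/50 (size 4.0%, power 70.1%).

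The cost is a text amendment to both documents, with no extra patients. The downside is a less favourable stated power or alpha.

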The good safety profile observed in this study is probably related to the confined nature of the biological cascade of events triggered by the near infra red activation of TOOKAD® Soluble in the target tissue vasculature. In contrast to other focal techniques which utilize non-selective thermal radiation, this cascade of events rapidly results in the occlusion and destruction of small vessels followed by non-thermal coagulative necrosis of the target tissue with minimal thermal dispersion to surrounding tissues. This unique therapeutic effect was confirmed by the follow-up MRI obtained 7 days after the TOOKAD® Soluble VTP procedure that demonstrated confluent necrosis that closely contours the prostate capsule within the treated lobe. It is important to note that although extra-prostatic necrosis was seen in most treated subjects, it was usually minimal (mean volume = 2.98 mL) and of minimal clinical significance.

The completed Latin American trial (PCM304) was conducted to test the efficacy of TOOKAD® Soluble VTP treatment (applied as hemiablation) in men with larger volume cancers, including those with bilateral Gleason 3+3 and 3+4 cancer. The study showed similar results to those obtained in prior Phase II studies and thereby confirmed the treatment applicability to patients with more advanced cancers. Selection criteria and treatment parameters were compatible with those of the current trial (PCM204). In the intent to treat (ITT) population of 81 men, 12 men had Gleason 3+4 cancer and 69 had Gleason 3+3. In the ITT group, 60 (74%) had negative biopsies at 12 months, although 8 patients did not undergo end of protocol biopsy. Of the 73 evaluable per protocol patients who completed end of study 12-month biopsies, 58 (80%) had negative biopsies. Out of the 12 patients who had Gleason 3+4 cancer at entry, two were withdrawn prior to receiving the study drug because of a history of TURP (exclusion criteria) discovered during the pretreatment ultrasound examination of the prostate and two others did not have the Month

6 and Month 12 prostate biopsies because of adverse events (stroke and perineal pain respectively). As a result, only 8 patients had evaluable Month 6 and Month 12 prostate biopsies. Of those 8 evaluable patients with Gleason 3+4 prostate cancer treated, 8 (100%) had negative end of study biopsies (Detailed in Table # 1 in appendix 13). None underwent subsequent treatment over the study interval.

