**IPSS questionnaire**

Scores with at least 1 but not more than 50% missing items will be imputed using the formula:  $S = s \times T \div t$  where s is the observed score, S is the imputed score, T is the maximum total score for the IPSS and t is the maximum score possible from the completed questions. Missing total scores will be imputed using a multiple imputation method (Markov Chain Monte Carlo method).

Other missing data, including biopsy data, will not be replaced.

A subject with missing Month 12 biopsy will be counted as failure for the primary analysis.

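### The 83.6% planning rate comes from biopsied men only; if a missing Month 12 biopsy counts as failure, as one of two conflicting SAP rules says, it is not conservative and the stated power does not hold

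*Protocol*

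**What the plan says.** **Planning rate.** Protocol 10.1 first expects a true rate above 90%, without a source. It then limits the estimate to intermediate-risk men "who underwent the TOOKAD Soluble procedure and for whom biopsies were available after 12 months", and reports: "we identified a true response rate is greater than 83.6% with >80% posterior probability (assuming a beta-binomial model". It adopts 83.6% as the conservative choice and arrives at 44 men with fully evaluable data. The synopsis includes 50 men in order to obtain 44 evaluable.

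**SAP, Planned sample size.** "For an assumed true response rate of 83.6%, we can discount a response rate of 70% at a one-sided alpha of 10" per cent, with 80% power at 44 men. The SAP's primary efficacy analysis declares success at 35 or more responders out of 44.

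**The history (Protocol 2.2.4).** PCM304 entered 12 Gleason 3+4 men. Of these, "two were withdrawn prior to receiving the study drug because of a history of TURP", and two others had no Month 6 or Month 12 biopsy because of adverse events. As a result, "only 8 patients had evaluable Month 6 and Month 12 prostate biopsies". The outcome: "Of those 8 evaluable patients with Gleason 3+4 prostate cancer treated, 8 (100%) had negative end of study biopsies".

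**Missing Month 12 biopsy.** The SAP says two things:
- Under the heading on missing data: "A subject with missing Month 12 biopsy will be counted as failure for the primary analysis".
- Under Efficacy population, only men who supplied 12-month biopsy data are included, and the Efficacy analysis section uses that population for all efficacy analyses.

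**The concern.** A planning rate should be estimated on the same scoring as the endpoint it is used to power. The 83.6% describes men who reached biopsy. If the trial scores men who do not reach biopsy as failures, the rate it will observe is the biopsied-men rate multiplied by the share of men biopsied, which is lower.

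Since power is stated at no other rate, a reader cannot see how quickly it falls. A trial that misses its threshold partly through missing biopsies could then be read as a well-powered negative result.

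**Working it through.** The alpha level differs between protocol (5%) and SAP (10%). That is a separate matter, and the SAP's declared rule is used throughout.

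**1. Reproduce 83.6%.** The prior is not stated; assume uniform, Beta(1,1). With 8 of 8 responders the posterior is Beta(9,1).
- 20th percentile = 0.2^(1/9) = 0.8363.
- P(r > 0.836) = 1 − 0.836^9 = 0.8005.

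This matches the stated figure. Near alternatives do not: 7/7 gives 81.8%, 9/9 gives 85.1%, 10/10 gives 86.4%, and 8/8 with a Jeffreys prior gives 90.5%.

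**2. Count the men left out.** 12 entered − 2 withdrawn before drug − 8 biopsied = 2. By implication these two were treated.

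**3. Same quantity with those two as failures.** 8 of 10 with the uniform prior gives Beta(9,3).

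| | 8/8, Beta(9,1) | 8/10, Beta(9,3) |
|---|---|---|
| 20th percentile | 83.6% | 65.0% |
| Posterior mean | 90.0% | 75.0% |
| Posterior median | 92.6% | 76.4% |
| P(r > 70%) | 0.960 | 0.687 |
| P(r > 83.6%) | 0.801 | 0.265 |

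Over other priors, the 8/10 bound is 67.3% (Jeffreys) and 70.2% (near-zero prior); neither of these priors gives 83.6% from 8/8. If one man is scored a failure and the other left out (8/9, uniform prior), the bound is 72.9%.

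**4. Effect of the plan's own allowance.** Suppose all 50 − 44 = 6 non-evaluable men were scored as failures and the rest responded at 83.6%. The scored rate is 0.836 × 44/50 = 73.6%. Using instead PCM304's overall experience (8 of 81 without the final biopsy), it is 0.836 × 73/81 = 75.3%.

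**5. Power of the declared rule**, P(X ≥ c | n, r), exact binomial. If all 50 men are analysed, the cut-off must be re-derived from the SAP's criterion (one-sided 90% lower bound, rounded to 0.01, at least 70%). The SAP does not name the interval; assume exact. At 35/44 the bound is 0.696, which rounds to 0.70 and passes, as the SAP says. At 39/50 it is 0.687 (fails) and at 40/50 it is 0.709 (passes).

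| True scored rate | 35 of 44 | 40 of 50 |
|---|---|---|
| 83.6% | 82.6% | 81.3% |
| 80% | 61.7% | 58.4% |
| 75% | 30.9% | 26.2% |
| 73.6% | 23.9% | 19.5% |

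A Wilson interval would also give 35 of 44 but would accept 39 of 50 (bound 0.697). Power with 39 of 50 is 71.1% at 80% and 38.2% at 75%.

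**The case against.** **The efficacy population fits the planning rate.** If only men with 12-month biopsy data are analysed, a biopsied-only rate is the right one, and 10.1 sizes the trial on evaluable men. This stands, and it is why the point is conditional. It does not remove the opposite instruction in the missing-data section, which is written expressly for the primary analysis.

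**The restriction is disclosed.** True. What 10.1 omits is the count, the source and the prior.

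**A 20th percentile is cautious.** It is, relative to 8 of 8 or to an expectation above 90%. It allows for sampling error, but not for men who never reach biopsy.

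**The historical endpoint may be stricter.** PCM304 reports negative biopsies; here residual Gleason 3+3 counts as success. The true rate could therefore be higher on this trial's endpoint. But the biopsied men were already 8 of 8, and a man without a biopsy fails on either definition.

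**Extra men and replacement.** Including 50 protects the evaluable number, not the response rate when missing is failure. Protocol 5.5.6 lets the sponsor replace men lost before the month 3 biopsy, which may remove some early losses, but not later ones.

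**Stronger readings.** A reader might infer from 65.0% that the history points below the 70% null. It does not: 65.0% is a lower bound, and the posterior mean and median both exceed 70%. A reader might also infer that true power is near a coin toss, since averaging over the 8/10 posterior gives 45%. That projects a 20% loss from 2 of 10 men (exact 95% interval about 3% to 56%) and takes one side of an unsettled rule.

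**Conclusion.** The concern holds conditionally. 83.6% is a lower bound on the response rate among biopsied men. It matches the trial's endpoint only if men without a Month 12 biopsy are left out of the analysis. If they count as failures, it is not conservative and the 80% power does not hold: power of the SAP rule falls from 83% to 62% at a scored rate of 80% and to 31% at 75%. The plan's allowance of 6 in 50 would bring the scored rate to about 73.6% if all six were failures.

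The conclusion rests on three assumptions: that the source is 8/8 with a uniform prior (strongly inferred from the exact match, not stated), that the two unbiopsied men were treated (by subtraction), and that non-evaluable men in the step 4 illustration are men without a Month 12 biopsy. The documents do not support saying that 8/10 is simply the correct history, or that 83.6% was miscalculated.

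**What to change.** 1. Reconcile the SAP's Efficacy population and Efficacy analysis sections with its missing-biopsy rule, so that one rule governs the primary analysis. This comes first.
2. In Protocol 10.1 and SAP Planned sample size, state the count, source study and prior behind 83.6%, and that it is a 20th-percentile bound among biopsied men.
3. Give a source for the expectation above 90%, or remove it.
4. If missing counts as failure, remove the conservative label, report the 8/10 bound with its mean beside 83.6%, and restate power at the rates that apply: 83%, 62% and 31% at 83.6%, 80% and 75% for 35 of 44. If all 50 men are analysed, state the cut-off and interval method; 40 of 50 under the exact interval gives about 58% at 80% and 26% at 75%.
5. If missing men are left out, keep 83.6% and say that power refers to biopsied men only.

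N is unchanged. The cost is some rewording and a short table; the downside is a less favourable stated power.
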